8.4.7 Mean of 7-point SMBG

Schedule and Parameters

The mean of 7-point SMBG is defined as the area under the 7-point SMBG profile divided by the measurement time (i.e., time of the last point – time of the first point), and will be calculated using the trapezoidal method. It will not be calculated if more than 3 points in the profile are missing.

Table presentation

Mean of 7-point SMBG and change from baseline in mean of 7-point SMBG will be calculated and summarized by cohort and visit. In addition, 7-point SMBG data will be summarized by cohort, visit and time point.

Subject Listings

Detailed information of every measurement will be listed, by (in the order of) cohort, investigator site, subject and visit.

Graphical Presentation

For mean of 7-point SMBG, a Mean (SE) plot representing mean and SE for each cohort at each scheduled visit will be provided. In addition, a figure will be created to present the mean curve of 7-point SMBG (mean +/- SE at each time point over nominal time points), at screening, Visit 15 and Visit 28, by cohort.

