8 STATISTICAL METHODS

8.1 General Considerations

In this study, unless otherwise specified, all analyses will be performed in a descriptive manner by age cohort (including ‘Cohort 1’, ‘Cohort 2’, ‘Cohort 3’ and ‘Total’). The ‘Total’ group will include all subjects in the analysis population.

Where appropriate, all dimensions will be summarized in metric units, but listings will, in addition, represent values as collected.

For continuous variables, the number of subjects, mean, standard deviation, median, minimum, and maximum values will be displayed, as appropriate according to the type of data. The minimum and maximum will be displayed to the same number of decimal places that the data were recorded to. The mean and median will have 1 extra decimal place and the standard deviation will have 2 extra decimal places. The geometric mean and coefficient of variation (CV) will have 2 extra decimal places. Confidence interval (of the mean) will have the same decimal precisions as the mean.

For categorical variables, frequency counts and percentages of total for each category will be presented; missing values will be treated as a separate category, where appropriate. Percentage will be presented in 1 decimal place.

Visit specific data (e.g., 7-point SMBG or pulmonary function tests) will be summarized by analysis visit, which is defined based on the visit windows specified in Section 0

Non-visit specific data (e.g., hypoglycemic events or daily dose) will be summarized by study period and/or by time interval. See relevant sections for more details.

8.1.1 **Data Handling/Imputation Methods**

8.1.1.1 **Missing Data Imputation**

Unless otherwise specified, missing data other than start date of adverse events (AE) or start/end date of concomitant medications (CM) will not be imputed.

The imputation rules for start date of Aes and start/end date of CMs are as follows:

Adverse Events

- Start date
 - If the start date is completely missing, the start date is set to the date of first dose.
 - If the year is present and the month and day are missing or the year and day are present and the month is missing:

If year = year of first dose, then set month and day to month and day of first dose

Version Date: 17-Jan-2020

- If year < year of first dose, then set month and day to December 31.
- If year > year of first dose, then set month and day to January 1st.
- If the month and year are present and the day is missing:
 - If year = year of first dose and

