8.4.5 Fasting pre-breakfast SMBG and post-prandial SMBG

Schedule and Parameters

Fasting pre-breakfast SMBG and post-prandial SMBG at each meal will be measured daily throughout the study.

Table presentation

For each of the four parameters (fasting pre-breakfast SMBG and post-prandial SMBG at breakfast, lunch and dinner), average will be calculated at weekly intervals for the titration period and at monthly intervals for the extension period for each subject, and summarized by cohort. Same as for total daily dose and prandial dose, only data collected in the 2nd half of each interval (i.e., within 3 days prior to the each clinic visit in the titration period and within 2 weeks prior to each visit in the extension period) will be included in the analysis.

Baseline is defined as the average of all values collected prior to Visit 2. Change from baseline for a post-baseline time interval will be calculated as average of SMBG in the post-baseline time interval – baseline for each subject, and then summarized by cohort.

Graphical Presentation

For each of the four parameters, a Mean (SE) plot will be provided, presenting weekly average in the titration period and monthly average in the extension period (along with standard error) by cohort.

8.4.6 7-point SMBG

Schedule and Parameters

7-point SMBG (pre-meal and 120-150 minutes post-dose at breakfast, lunch and dinner as well as at bedtime) will be collected at screening visit, visits 6, 9, 12, 15 in the titration period, and visits 19, 22, 25, 28 in the extension period.

Table presentation

For each of the 7 parameters (pre-meal and 120-150 minutes post-dose 7-point SMBG at breakfast, lunch and dinner as well as at bedtime), average will be calculated at weekly intervals for the titration period and at monthly intervals for the extension period for each subject, and summarized by cohort. For each of these intervals, all data collected from the date of the previous on-site visit (including) to 1 day before the current visit for each visit are included in the summary.

Baseline is defined as the average of all values collected prior to Visit 2. Change from baseline for a post-baseline time interval will be calculated as average of 7-point SMBG in the post-baseline time interval – baseline for each subject, and then summarized by cohort.

Subject Listings

Detailed information of every measurement will be listed, by (in the order of) cohort, investigator site, subject and visit.

Graphical Presentation

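### The mean of the 7-point glucose profile is calculated with any 3 of 7 readings missing, so it can omit every post-dose or every pre-meal reading and be off by about half the post-meal rise

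*SAP*

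**What the plan says.** SAP 8.4.6 gives the seven points as "pre-meal and 120-150 minutes post-dose at breakfast, lunch and dinner as well as at bedtime": three pre-meal, three post-dose and one bedtime.

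SAP 8.4.7 reduces each profile to one number, "defined as the area under the 7-point SMBG profile divided by the measurement time", where measurement time runs from the first to the last available point. The area "will be calculated using the trapezoidal method". The only condition for calculating it is: "It will not be calculated if more than 3 points in the profile are missing". The section does not say which points must be present. SAP 8.1.1.1 rules out filling the gaps: "Unless otherwise specified, missing data other than start date of adverse events (AE) or start/end date of concomitant medications (CM) will not be imputed".

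On reporting, SAP 8.4.7 states: "Mean of 7-point SMBG and change from baseline in mean of 7-point SMBG will be calculated and summarized by cohort and visit". It adds: "In addition, 7-point SMBG data will be summarized by cohort, visit and time point".

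**The concern.** The rule counts missing points but ignores which ones they are. Exactly three points are post-dose, so a profile that lacks all of them passes. So does one that lacks all three pre-meal points, or one that stops after lunch. With no imputation, the trapezoid runs straight across each gap.

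Pre-meal and post-dose glucose usually differ systematically, so a profile made up mostly of one kind does not estimate average glucose over the day. Two values of the same parameter may then differ only because different readings were taken. At stake are the by-visit mean and its change from baseline (Table 14.4.4.2, Figure 14.4.1.2), in cohorts planned at 14 to 18 subjects.

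**Working it through.** The documents give no value for this parameter to reproduce, no expected post-meal rise, no meal times for the profile and no expected missingness. The levels and clock times below are assumptions.

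**1. General result.** In trapezoidal integration each reading is weighted by half the length of its adjoining intervals. The readings run pre, post, pre, post, pre, post, bedtime, so each of the six intervals has exactly one post-dose end. The post-dose readings together therefore carry half the total weight, whatever the meal times. Let pre-meal and bedtime glucose equal L and post-dose glucose equal L + R:

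- full mean = L + R/2
- mean without post-dose points = L
- error = −R/2

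**2. Worked profiles.** Assumed times are 7:30, 10:00, 12:00, 14:30, 18:00, 20:30 and 22:00 (span 14.5 h). Assumed levels (pre-meal / post-dose / bedtime, mg/dL):

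- Pattern A, 105/145/125. The first two are midpoints of the fasting target of 80 to 130 (Protocol 8.1.7) and the dose-maintenance band of 110 to 180 (Protocol 8.1.4, Table 2). The rise is 40.
- Pattern B, 140/200/170. It has no source in the documents. The rise is 60.

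Pattern A:

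- Full: (2.5×125 + 2×125 + 2.5×125 + 3.5×125 + 2.5×125 + 1.5×135)/14.5 = 1827.5/14.5 = 126.0
- No post-dose points: (4.5×105 + 6×105 + 4×115)/14.5 = 1562.5/14.5 = 107.8
- No pre-meal points (span now 12 h): (4.5×145 + 6×145 + 1.5×135)/12 = 1725/12 = 143.8
- Post-lunch only missing: the 6 h from 12:00 to 18:00 fall by 20 on average, so −120/14.5 = −8.3
- Pre-dinner only missing: the 6 h from 14:30 to 20:30 rise by 20 on average, so +8.3

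Pattern B is computed the same way: full mean 2487.5/14.5 = 171.6.

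| Missing | Error, A | Error, B |
|---|---|---|
| All three post-dose | −18.3 | −27.4 |
| All three pre-meal | +17.7 | +26.6 |
| Post-lunch only | −8.3 | −12.4 |
| Pre-dinner only | +8.3 | +12.4 |
| Last three points | −1.0 | −1.6 |

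With bedtime midway between the two levels, the post-dose factor is 18.3/40 = 27.4/60 = 0.46, slightly under one half. Of the 35 ways to lose three points, 13 (A) and 18 (B) shift the mean by at least 10 mg/dL, while 14 and 12 shift it by less than 5. Losing the last three points barely moves the value here because high and low readings alternate, but the result then covers only 7 of 14.5 hours.

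**3. Range from the documents' own bands.** Take pre-meal and bedtime from 80 to 130 and post-dose from 110 to 180, all post-dose points missing, error = −(post − pre)/2:

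- 80 with 180: −50
- 105 with 145: −20
- 130 with 180: −25
- 130 with 110: +10

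**4. Change from baseline.** With a complete screening profile and a later profile without pre-meal points, pattern A shows a change of +17.7 although glucose is unchanged. If the same points are missing at both visits and the rise is unchanged, the errors cancel. If post-dose points are missing at both, a real change in post-meal glucose goes unseen.

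**5. Effect on a cohort mean.** One affected profile moves it by 18/14 = 1.3 to 27/14 = 1.9 mg/dL (n = 14), or 18/18 = 1.0 to 27/18 = 1.5 mg/dL (n = 18).

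**The case against.** A reader might infer that the reported means will be 18 to 27 mg/dL too low. The documents do not support that. The figure needs an assumed rise of 40 to 60 mg/dL. The 80 to 130 band is a fasting target, not a pre-lunch or pre-dinner level, and the 110 to 180 band is where a 3-day median leaves the dose unchanged, not an expected post-meal level. Nor is the direction fixed. On treatment, post-dose readings are required at every meal and drive titration (Protocol 9.2.6.2), whereas pre-lunch and pre-dinner readings are needed only for the weekly profile. Missing pre-meal points, which push the mean up, are at least as plausible.

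A reader might also infer that the reported changes from baseline will be false. That requires missing patterns that differ between visits, and the documents say nothing about how often this will happen.

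The parameter also carries little weight. It sits under Other Endpoints, is descriptive, and is not marked for the DMC package. The titration objective rests on the 120 to 150 minute readings, which SAP 8.4.5 analyses directly. Each of the seven points is also summarised, plotted and listed separately, so an attentive reader could see an imbalance.

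All of this stands and limits the priority. It does not remove the defect: the separate summaries leave the mean uncorrected, and the number of subjects displayed beside it does not separate complete profiles from profiles with only four points.

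**Conclusion.** The point holds at minor priority. Followed exactly, SAP 8.4.7 yields a mean from profiles that contain no post-dose reading, no pre-meal reading, or only part of the day. That the error is about half the post-meal rise follows from the trapezoidal formula when bedtime glucose is near the pre-meal level. The figure of about 18 to 27 mg/dL in either direction depends on the assumed clock times and an assumed rise of 40 to 60 mg/dL. Combining the fasting target with the dose-maintenance band widens the range to about −50 to +10 mg/dL for missing post-dose points. How far any cohort mean or change from baseline is affected depends on how many profiles are incomplete and whether the pattern differs between visits, which the documents do not indicate.

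**What to change.** Replace the missing-point rule in SAP 8.4.7 with one on composition: calculate the mean only if the pre-breakfast and bedtime points are present, at most one pre-meal reading is missing (pre-lunch or pre-dinner), and at most one post-dose reading is missing. Otherwise set it to missing.

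Under patterns A and B, the worst case among the permitted profiles falls from about 18 to 27 mg/dL to about 8 to 12 mg/dL (post-lunch alone missing, or pre-dinner alone missing), and every calculated mean then runs from pre-breakfast to bedtime. Because this reduces the error without removing it, add a sensitivity summary of the mean and its change from baseline restricted to complete 7-point profiles. Its subject counts would also show how many profiles are complete.

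The cost is one revised sentence and one added summary. The downside is fewer evaluable profiles in cohorts of 14 to 18. No change to data collection is needed.

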8.4.8 Insulin to carbohydrate ratio

Insulin to carbohydrate ratio for each meal will be captured at the screening visit, and at end of treatment/early termination visit for the titration period. Data will be listed, by (in the order of) cohort, investigator site, subject and visit.

8.4.9 Substance Use

Pre-trial usage of tobacco and alcohol will be captured at screening. Data will be listed, by (in the order of) cohort, investigator site, and subject.

9 CHANGES FROM PREVIOUS VERSIONS

REVISION NUMBER	AUTHOR	EFFECTIVE DATE	CHANGES:	REASON:
1.1	[name]	2017/10/20	Remove all description regarding the 2 previous subjects from the Sanofi study.	The 2 subjects will not be included in the any of the analyses
1.1	[name]	2017/10/20	Present PK concentrations/parameters by dose	The PK concentrations and parameters of insulin and FDKP are affected by the dose of AFREZZA®
1.1	[name]	2017/10/20	Change ‘clinically relevant decline’ in pulmonary function to ‘verified clinically relevant decline’, and add a table to summarize the duration of verified clinically relevant decline.	Clinically relevant decline will be verified by the sites. The duration of such decline is of interest
1.1	[name]	2017/10/20	Add a table to present the use of post-meal dose.	It is of interest to see how frequently post-meal (i.e., supplemental) doses need to be given
1.1	[name]	2017/10/20	Adjust visit windows	From clinical point of view, it doesn’t make sense to use very large windows
1.1	[name]	2017/10/20	Add ‘Early Termination’ visit to the by-visit summary tables	To draw special attention to data collected at the early termination visit. If there is some particular data pattern associated with subject discontinuation, it could be more easily recognized.
1.1	[name]	2017/10/20	Create a summary table for ‘documented hypoglycemia’ (defined as glucose < 70 mg/dl), including the subcategories of asymptomatic/symptomatic documented hypoglycemia	This category of hypoglycemia is of interest from medical point of view.
1.1	[name]	2017/10/20	When calculating average dose/SMBG at weekly interval in the titration period and at monthly interval in the extension period, only include data collected in the 2 nd half of the interval (i.e., within 3 days prior to the each clinic visit in the titration period and within 2 weeks prior to each visit in the extension period) in the analysis.	These values are more of interest from clinical point of view.

REVISION NUMBER	AUTHOR	EFFECTIVE DATE	CHANGES:	REASON:
3.0	[name]	2019/12/10	Add the imputation rules of incomplete T1DM diagnosis date for the calculation of duration of T1DM	As analysis needed
3.0	[name]	2019/12/10	Add “Drug-related serious TEAEs” item for TEAE overall summary	To show the number and percentage of subjects who has any drug-related serious TEAEs in the AE overall summary table
3.0	[name]	2019/12/10	Correct the derivation of time profile of hypoglycemia to be “The number of days in the time interval which are between first dose date and last dose date (both inclusive) /30.4375”	Correct the derivation error.
3.0	[name]	2019/12/10	Use “Benzoylecgonine”to replace Cocaine” in the table of Urinary Laboratory tests	It was captured in the CRF of “Benzoylecgonine”, not “Cocaine”.
3.0	[name]	2019/12/10	Add “the result of sinus rhythm test” in the summarization of ECG parameters as it is captured in the EDC.	Updated as EDC data
3.0	[name]	2019/12/10	Add the section 8.4.6 “7-point SMBG” , at the same time, change the old 8.4.6 “7-point SMBG” to be 8.4.7 “Mean of 7-point SMBG	Add some analyses for the 7-point SMBG parameters and keep those analyses we proposed for Mean of 7-point SMBG
3.0	[name]	2019/12/10	Appendix 3 has been updated	Updated as the shell updates

APPENDIX 1 LIST OF LAB UNITS

Panel/Test	Conventional Units	SI Units
Albumin / Creatinine Ratio	mg/mmol Creatinine	mg/mmol Creatinine
C Peptide	ng/mL	nmol/L
Chemistry / ALT	U/L	U/L
Chemistry / AST	U/L	U/L
Chemistry / Albumin	g/dL	g/L
Chemistry / Alkaline Phosphatase	U/L	U/L
Chemistry / BUN	mg/dL	mmol/L
Chemistry / Bicarbonate	mEq/L	mmol/L
Chemistry / Bilirubin, Direct	mg/dL	mcmol/L
Chemistry / Bilirubin, Total	mg/dL	mcmol/L
Chemistry / Calcium	mg/dL	mmol/L
Chemistry / Chloride	mEq/L	mmol/L
Chemistry / Cholesterol, Total	mg/dL	mmol/L
Chemistry / Creatine Phosphokinase (CPK)	U/L	U/L
Chemistry / Creatinine	mg/dL	mcmol/L
Chemistry / Lactate Dehydrogenase	U/L	U/L
Chemistry / Phosphorous	mg/dL	mmol/L
Chemistry / Potassium	mEq/L	mmol/L
Chemistry / Protein	g/dL	g/L
Chemistry / Sodium	mEq/L	mmol/L
Chemistry / Triglyceride	mg/dL	mmol/L
Chemistry / Uric Acid	mg/dL	mmol/L
Creatinine, Urine	mg/dL	mmol/L
Glucose	mg/dL	mmol/L

Version Date: 17-Jan-2020

Panel/Test	Conventional Units	SI Units
HDL	mg/dL	mmol/L
Hematology / Basophils	K/cu mm	$\times 10^9/L$
Hematology / Eosinophils	K/cu mm	$\times 10^9/L$
Hematology / Hematocrit	%	%
Hematology / Hemoglobin	g/dL	g/L
Hematology / Lymphocytes	K/cu mm	$\times 10^9/L$
Hematology / MCH	pg	pg
Hematology / MCHC	g/dL	g/dL
Hematology / MCV	fl	fl
Hematology / MPV	fl	fl
Hematology / Monocytes	K/cu mm	$\times 10^9/L$
Hematology / Platelet	K/cu mm	$\times 10^9/L$
Hematology / RBC	$\times 10^6/cu\ mm$	$\times 10^{12}/L$
Hematology / RDW	%	%
Hematology / Total Neutrophils	K/cu mm	$\times 10^9/L$
Hematology / WBC	K/cu mm	$\times 10^9/L$
Hemoglobin A1c	%	%
LDL	mg/dL	mmol/L

APPENDIX 2 GLOSSARY OF ABBREVIATIONS

AE	Adverse Event
AESI	Adverse Event of Special Interest
ATC	Anatomic Therapeutic Classification
BMI	Body Mass Index
BLQ	Below Limit of Quantification
CM	Concomitant Medications
CRF	Case Report Form
CV	Coefficient of Variation
DMC	Data Monitoring Committee
ECG	Electrocardiogram
FDA	Food and Drug Administration
FDKP	Fumaryl Diketopiperazine
FEV ₁	Forced Expiratory Volume in 1 Second
ICF	Informed Consent Form
IA	Interim Analyses
LLQ	Lower Limit of Quantification
MDI	Multiple Daily Injections
PK	Pharmacokinetic
RAA	Rapid-Acting Analog
SAP	Statistical Analysis Plan
SAE	Serious Adverse Event
SC	Subcutaneous
SD	Standard Deviation
SE	Standard Error
SMBG	Self-Monitored Blood Glucose
TEAE	Treatment-Emergent Adverse Event
T1DM	Type 1 Diabetes Mellitus

APPENDIX 3 LIST OF TABLES, FIGURES, LISTINGS, AND ANALYSES

List of Tables		Include in DMC
Patient Disposition		
Table 14.1.1.1	Overall Disposition – All Screened Subjects	X
Table 14.1.1.2	Protocol Deviations – Safety Population	
Demographics and Baseline Characteristics		
Table 14.1.1.3	Demographics and Baseline Characteristics – Safety Population	X
Table 14.1.1.3.1	Demographics and Baseline Characteristics – PK Population	X
Table 14.1.1.4	Medical History – Safety Population	X
Other Baseline Measurements		
Table 14.1.1.5	Summary of 12-Lead Electrocardiogram at Screening – Safety Population	
Treatment and Medications		
Table 14.1.2.1	Prior Medications – Safety Population	
Table 14.1.2.2	Concomitant Medications – Safety Population	
Table 14.1.2.3	Duration of Exposure – AFREZZA [®] – Safety Population	
Table 14.1.2.4	AFREZZA [®] Dose (U) at PK Visit – PK Population	X
Table 14.1.2.5	Average Total Daily Dose of AFREZZA [®] (U) (eDiary Data) – Safety Population	X
Table 14.1.2.5.1	Average Total Daily Dose of AFREZZA [®] (U) by Starting Dose for Cohort 1 and Cohort 2 (eDiary Data) – Safety Population	X
Table 14.1.2.6	Average Prandial Dose of AFREZZA [®] (U) by Meal (eDiary Data) – Safety Population	X
Table 14.1.2.6.1	Average Prandial Dose of AFREZZA [®] (U) by Meal by Starting Dose for Cohort 1 and Cohort 2 (eDiary Data) – Safety Population	X
Table 14.1.2.7	Summary of Use of Post-meal Doses (eDiary Data) – Safety Population	X
Pharmacokinetic		

Table 14.2.1.1	Summary of Serum Insulin Concentrations by PK Dose of AFREZZA [®] and Scheduled Time Point– PK Population	X
Table 14.2.1.2	Summary of Serum FDKP Concentrations by PK Dose of AFREZZA [®] and Scheduled Time Point – PK Population	X
Table 14.2.2.1	Summary of Insulin Pharmacokinetic Parameters by PK Dose of AFREZZA [®] – PK Population	X
Table 14.2.2.2	Summary of FDKP Pharmacokinetic Parameters by PK Dose of AFREZZA [®] – PK Population	X
Table 14.2.3.1	Summary of Blood Glucose Values Collected at the PK Visit by Scheduled Time Point– PK Population	X
Safety		
Table 14.3.1.1	Overall Summary of Treatment-Emergent Adverse Events – Safety Population	
Table 14.3.1.2	Treatment-emergent Adverse Events by System Organ Class and Preferred Term – Safety Population	X
Table 14.3.1.2.1	Treatment-emergent Adverse Events by Preferred Term Only – Safety Population	
Table 14.3.1.3	Treatment-emergent Adverse Events by Relationship to Study Drug and System Organ Class/Preferred Term – Safety Population	
Table 14.3.1.4	Treatment-emergent Adverse Events by Severity and System Organ Class/Preferred Term – Safety Population	
Table 14.3.1.5	Most Common Treatment-emergent Adverse Events Where Preferred Term Is $\geq 5\%$ – Safety Population	
Table 14.3.1.6	Treatment-emergent Serious Adverse Events by System Organ Class and Preferred Term – Safety Population	X
Table 14.3.1.7	Treatment-emergent Serious Adverse Events by Relationship to Study Drug and System Organ Class/Preferred Term – Safety Population	
Table 14.3.1.8	Treatment-emergent Adverse Events Leading to Study Discontinuation by System Organ Class and Preferred Term – Safety Population	
Table 14.3.1.9	Treatment-emergent Adverse Events Leading to Death by System Organ Class and Preferred Term – Safety Population	
Table 14.3.1.10	Treatment-emergent Adverse Events Leading to Temporary Treatment Interruption by	

	System Organ Class and Preferred Term – Safety Population	
Table 14.3.1.11	Treatment-emergent Adverse Events of Special Interest by System Organ Class/Preferred Term – Safety Population	
Table 14.3.1.12	Treatment-emergent Adverse Events of Special Interest by Relationship to Study Drug and System Organ Class/Preferred Term – Safety Population	
Table 14.3.2.1	Summary of Hypoglycemic Events – Safety Population	X
Table 14.3.2.2	Summary of Causality of Hypoglycemic Events – Safety Population	
Table 14.3.3.1	Value and Change from Baseline in Vital Signs – Safety Population	X
Table 14.3.4.1	Value and Change from Baseline in FEV ₁ – Safety Population	X
Table 14.3.4.2	Summary of Clinically Relevant Decline from Baseline in Pulmonary Function – Safety Population	X
Table 14.3.4.3	Summary of Duration of Verified Clinically Relevant Decline from Baseline in Pulmonary Function– Safety Population	
Table 14.3.5.1	Shift Table for Anti-insulin Antibody – Safety Population	X
Other		
Table 14.4.1.1	Value and Change from Baseline in HbA1c (%) – Safety Population	
Table 14.4.2.1	Average of Value and Change from Baseline in Fasting pre-breakfast SMBG (mg/dL) (eDiary Data) – Safety Population	
Table 14.4.3.1	Average of Value and Change from Baseline in Post-prandial SMBG (mg/dL) by Meal (eDiary Data) – Safety Population	
Table 14.4.4.1	Summary of 7-Point SMBG (mg/dL) by Time Point and Visit (eDiary Data) – Safety Population	
Table 14.4.4.2	Value and Change from Baseline in Mean of 7-Point SMBG (mg/dL) (eDiary Data) – Safety Population	

List of Listings		Include in DMC
Patient Disposition		
Listing 16.2.1.1	Overall Disposition – Safety Population	X
Listing 16.2.2.1	Inclusion/Exclusion Criteria – All Screened Subjects	
Listing 16.2.2.2	Protocol Deviations – Safety Population	
Listing 16.2.2.3	Analysis Sets – All Enrolled Subjects	
Demographics and Baseline Characteristics		
Listing 16.2.4.1	Demographics and Baseline Characteristics – Safety Population	X
Listing 16.2.4.2	Medical History – Safety Population	X
Other Baseline Measurements		
Listing 16.2.4.3	12-Lead Electrocardiogram at Screening – Safety Population	
Listing 16.2.4.4	Fasting Serum C-Peptide at Screening – Safety Population	
Listing 16.2.4.5	Laboratory Results at Screening – Hematology – Safety Population	
Listing 16.2.4.6	Laboratory Results at Screening – Chemistry – Safety Population	
Listing 16.2.4.7	Laboratory Results at Screening – Urinalysis – Safety Population	
Listing 16.2.4.8	Serology Tests at Screening – Safety Population	
Listing 16.2.4.9	Urine Drug Screen at Screening – Safety Population	
Listing 16.2.4.10	Tobacco Usage at Screening – Safety Population	
Listing 16.2.4.11	Alcohol Usage at Screening – Safety Population	
Treatment and Medications		
Listing 16.2.5.1	Prior and Concomitant Medications – Safety Population	
Listing 16.2.5.2	Drug Accountability – Safety Population	
Listing 16.2.5.3	AFREZZA [®] Dose (U) at PK Visit – PK Population	X
Pharmacokinetic		
Listing 16.2.6.1	Serum Pharmacokinetic Concentrations – Insulin – PK Population	X

Listing 16.2.6.2	Serum Pharmacokinetic Concentrations – FDKP – PK Population	X
Listing 16.2.6.3	Pharmacokinetic Parameters – Insulin – PK Population	X
Listing 16.2.6.4	Pharmacokinetic Parameters – FDKP – PK Population	X
Listing 16.2.6.5	Blood Glucose Values at PK Visit – PK Population	X
Safety		
Listing 16.2.7.1	Adverse Events – Safety Population	
Listing 16.2.7.2	Treatment-emergent Adverse Events – Safety Population	X
Listing 16.2.7.3	Prior and Follow-up Adverse Events – Safety Population	
Listing 16.2.7.4	Treatment-emergent Serious Adverse Events – Safety Population	X
Listing 16.2.7.5	Treatment-emergent Adverse Events Leading to Study Discontinuation – Safety Population	
Listing 16.2.7.6	Treatment-emergent Adverse Events Leading to Death – Safety Population	
Listing 16.2.7.7	Treatment-emergent Adverse Events Leading to Temporary Treatment Interruption – Safety Population	
Listing 16.2.7.8	Treatment-emergent Adverse Events of Special Interest – Safety Population	
Listing 16.2.7.9	Death – Safety Population	X
Listing 16.2.7.10	Hypoglycemic Events – Safety Population	X
Listing 16.2.7.11	Severe Hypoglycemic Events – Safety Population	X
Listing 16.2.7.12	Cough – Safety Population	X
Listing 16.2.8.1	Vital Signs – Safety Population	X
Listing 16.2.8.2	Physical Examinations – Safety Population	X
Listing 16.2.8.3	Spirometry Tests – Safety Population	X
Listing 16.2.8.4	Anti-insulin Antibody – Safety Population	X
Listing 16.2.8.5	Urine Cotinine Tests – Safety Population	
Listing 16.2.8.6	Female Reproductive Status -- Safety Population	
Listing 16.2.8.7	Pregnancy Tests -- Safety Population	
Other		
Listing 16.2.9.1	7-Point SMBG (eDiary Data) – Safety Population	
Listing 16.2.9.2	HbA1c – Safety Population	

Listing 16.2.9.3	Insulin to Carbohydrate Ratio – Safety Population	
------------------	---	--

List of Figures		Include in DMC
Treatment		
Figure 14.1.1.1	Average Daily total dose of AFREZZA [®] (eDiary Data) -- Safety Population	
Figure 14.1.1.2	Average Prandial Dose of AFREZZA [®] by Meal (eDiary Data) -- Safety Population	
Figure 14.1.1.3	Total Daily Post-Prandial Dose of AFREZZA [®] Over Time (eDiary Data) -- Safety Population	
Pharmacokinetic		
Figure 14.2.1.1	Mean of Baseline-Corrected Serum Insulin Concentrations Over Time by PK Dose of AFREZZA [®] – PK Population	X
Figure 14.2.1.2	Individual Patient Profile of Baseline-Corrected Serum Insulin Concentrations Over Time – PK Population	X
Figure 14.2.2.1	Mean of Serum FDKP Concentrations Over Time by PK Dose of AFREZZA [®] – PK Population	X
Figure 14.2.2.2	Individual Patient Profile of Serum FDKP Concentrations Over Time – PK Population	X
Figure 14.2.3.1	Mean of Blood Glucose Levels Over Time at PK Visit – PK Population	X
Figure 14.2.3.2	Individual Patient Profile of Blood Glucose Levels Over Time at PK Visit – PK Population	X
Safety		
Figure 14.3.1.1	Day Profile of Hypoglycemic Events – Safety Population	
Figure 14.3.1.2	Time Profile of Hypoglycemic Events in Relation to Pre-meal Dosing Time – Safety Population	
Figure 14.3.2.1	Day Profile of Cough – Safety Population	
Other		
Figure 14.4.1.1	Average SMBG by Meal and Time Point (eDiary Data) – Safety Population	
Figure 14.4.1.2	Mean of 7-Point SMBG (eDiary Data) – Safety Population	
Figure 14.4.1.3	Average of 7-Point SMBG by Time Point (eDiary Data) – Safety Population	

Figure 14.4.1.4	HbA1c – Safety Population	
Figure 14.4.2.1	BMI – Safety Population	

